## **VII. ADVERSE EVENTS:**

Reports of all adverse events will be made and recorded for the duration of the study, and categorized as specific to those complications associated with femoral access, such as hematoma, bleeding, and other vascular access complications. Those complications not related to vascular access will be stored locally only.

Adverse events will be recorded on the case report forms (CRF) and adjudicated by the site Principal Investigator as to their severity and whether or not directly, indirectly, or not connected to the study devices, and forwarded to the Data Center for entry into the database.

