#### Serious Adverse Event

A serious adverse event (SAE) is defined as an adverse event that:

- Led to death,
- Led to a serious deterioration in health that either,
  - Resulted in a life-threatening illness or injury, or
  - Resulted in a permanent impairment of a body structure or a body function, or
  - Required in-patient hospitalization, or
  - Resulted in medical or surgical intervention to prevent life threatening illness or injury or permanent impairment to a body structure or a body function.

Note: This includes device deficiencies that might have led to a serious adverse event if (a) suitable action had not been taken or (b) intervention had not been made or (c) if circumstances had been less fortunate.

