## **VIII. DATA MANAGEMENT**

#### Data Collection Process

Data will be collected in an anonymized (coded) fashion using case report forms for each subject. CRFs will be transmitted to the data center for entry in to the database. Data may be collected by clinical research personnel assigned to the study, under the supervision of the investigator.

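### The adverse event section contradicts itself on whether complications unrelated to vascular access, serious ones and deaths included, enter the central database

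*Combined protocol and SAP*

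**What the plan says.** Section VII (Adverse Events) opens broadly: "Reports of all adverse events will be made and recorded for the duration of the study". It names a femoral access category, "such as hematoma, bleeding, and other vascular access complications", and then sets the rest apart: "Those complications not related to vascular access will be stored locally only".

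The second paragraph of Section VII carries no such limit. Adverse events go on the CRF, are "adjudicated by the site Principal Investigator as to their severity and whether or not directly, indirectly, or not connected to the study devices", and are then "forwarded to the Data Center for entry into the database". Section VIII (Data Collection Process) agrees: "CRFs will be transmitted to the data center for entry in to the database".

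The Serious Adverse Event subsection gives a definition ("A serious adverse event (SAE) is defined as an adverse event that", followed by a list that includes death) but no reporting route. In Section IV the assignment becomes known when the envelope is opened after Perclose deployment, and no masking is described. In Section VI the only safety outcome given its own between-arm analysis is hematoma.

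**The concern.** Site staff cannot obey both paragraphs of Section VII for an event outside the access category. One paragraph keeps it at the site and the other sends it on. Nothing says which governs, and seriousness makes no difference.

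What is at stake is the completeness of safety reporting. The Clinical Need text in Section I says the patch has not been studied together with a closure device, so a full count of serious events by arm is a reasonable thing to expect from this trial. Under the local-storage sentence, events are sorted by relatedness before they reach the database, in a trial with no described masking. Being access-related is also not the same as being device-related. An event connected to a study device but classed as non-access would stay at the site too.

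**Working it through.** **1. The passages side by side**

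| Event | If the local-storage sentence governs | If the forwarding paragraph governs |
|---|---|---|
| Access complication, device-connected or not | Data Center | Data Center |
| Non-access complication, not serious | Site only | Data Center |
| Non-access serious event or death | Site only | Data Center |
| Device-connected event classed as non-access | Site only | Data Center |

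The two readings differ in every row but the first. The forwarding paragraph expressly covers events found unconnected to the devices, so it cannot simply be read as limited to related events. Section VIII does not settle the matter, because it does not say whether locally stored complications appear on the forwarded CRFs. The CRF appendix is not in the text available, so its adverse event fields are unknown.

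**2. Who classifies**

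Section VII gives the site Principal Investigator two judgements, severity and device connection. It names no one to decide whether an event is related to vascular access, and gives no criteria beyond an open-ended list of examples.

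**3. The plan's own figure**

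Inputs from Section VI: 50 patients, difference 10 min, SD 10 min, two-sided alpha 0.05. The allocation ratio is not stated, so 25 per arm is assumed.

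- Standardized difference: 10 / (10 × √(2/25)) = 3.536.
- Normal approximation: Φ(3.536 − 1.960) = Φ(1.576) = 94.2%. The t test gives 93.4%.

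The stated power above 90% reproduces. Nothing in it depends on where adverse events are stored.

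**4. Size of one missing event**

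This is a scale only. The documents give no rate for non-access events.

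- At 25 per arm: 1/25 = 4 percentage points. For arms of 24 to 26 (two blocks of 25, each split 12/13): 1/24 = 4.2 to 1/26 = 3.8 points.
- Exact two-sided 95% upper limit for 0/25: 1 − 0.025^(1/25) = 13.7%. For 0/24 it is 14.2% and for 0/26 it is 13.2%. For 1/25 it is about 20.4%.
- So recording 1/25 as 0/25 lowers the upper limit from about 20.4% to 13.7%.

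**5. What complete data could show**

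Fisher's exact test, 25 per arm, two-sided:

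- 5 versus 0: 2 × C(25,5)/C(50,5) = 2 × 53,130/2,118,760 = 0.0502.
- 6 versus 0: 2 × C(25,6)/C(50,6) = 2 × 177,100/15,890,700 = 0.022.
- At assumed illustrative rates, power is about 2% for 3% versus 10%, and about 7% for 5% versus 15%.

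Even a complete database therefore supports only a descriptive table of serious events.

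**The case against.** The strongest reply is that the plan does not clearly exclude anything. A reader might infer from the local-storage sentence that non-access events never reach the database. The documents do not support that as settled, because the forwarding paragraph and Section VIII point the other way.

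A reader might also infer that an unmasked investigator decides what is access-related. The text does not say so. The investigator is named for severity and device connection, and an access complication judged unconnected to the patch is forwarded on either reading.

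A third tempting inference is that deaths, strokes or embolic events cannot be compared by arm. That is too strong. All adverse events must be recorded somewhere, a site log links identity to study number (Data Confidentiality), records are kept for 2 years, source data must be open to monitors and auditors, and Section IV describes a single site (Section VI speaks of centers). Some embolic events, or a death from access bleeding, could also fall within the access category. Stroke and embolism are not named as outcomes.

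Finally, the 4-point figure would fit any one missing event in any trial of this size, so it does not measure this defect.

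All of this stands as a limit on the claim. It does not remove the contradiction, the lack of an exception for serious events, or the missing criteria. Retrieval depends on someone deciding to do it, and Section IX lets files be destroyed once retention ends.

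**Conclusion.** The concern holds as an unresolved contradiction with a practical consequence. If the local-storage sentence is followed, the central database omits events classed as non-access, under no stated criteria or masked review, and a by-arm table of serious events drawn from it could be incomplete unless local records are added. It does not show that events are lost, or that any arm comparison would be biased in a known direction.

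The effect is confined to safety completeness. Time to hemostasis and its power are untouched, and hematoma is expressly an access complication. The numerical scale assumes near-equal arms of about 25 and no particular event rate. The inference that those classifying events may know the arm rests on the absence of any described masking. The change is worth making because it costs little and removes a rule that, followed as written, would leave gaps in the safety data.

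**What to change.** Delete the local-storage sentence from Section VII, so that its two paragraphs and Section VIII agree. State that all adverse events, or at minimum all serious adverse events and deaths, go to the Data Center for every randomized subject. Record access-relatedness and device-relatedness as two separate coded fields, used to describe events and not to decide whether they are sent. Add one line to Section VI: serious events will be tabulated by randomized arm regardless of relatedness, as a descriptive summary.

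The cost is a few more CRF entries over about one day of observation in 50 subjects. Section VII already requires all adverse events to be recorded, so no extra assessment or adjudicator is needed.

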### Adverse Event

Any clinically relevant event that occurs during the performance of the study that puts the subject at additional risk of injury, whether foreseen or not, and requires additional care beyond that expected as a result of the study.

### Adverse Device Event

An adverse event related to the use of the device. This includes adverse events resulting from insufficient or inadequate instructions for use, deployment, or operation, or any malfunction of

the device. This definition also includes any event resulting from user error or from intentional misuse of the device by the investigator.

#### Serious Adverse Event

A serious adverse event (SAE) is defined as an adverse event that:

- Led to death,
- Led to a serious deterioration in health that either,
  - Resulted in a life-threatening illness or injury, or
  - Resulted in a permanent impairment of a body structure or a body function, or
  - Required in-patient hospitalization, or
  - Resulted in medical or surgical intervention to prevent life threatening illness or injury or permanent impairment to a body structure or a body function.

Note: This includes device deficiencies that might have led to a serious adverse event if (a) suitable action had not been taken or (b) intervention had not been made or (c) if circumstances had been less fortunate.

## **VIII. DATA MANAGEMENT**

#### Data Collection Process

Data will be collected in an anonymized (coded) fashion using case report forms for each subject. CRFs will be transmitted to the data center for entry in to the database. Data may be collected by clinical research personnel assigned to the study, under the supervision of the investigator.

#### Data Confidentiality

Subject data will be collected in an anonymous form. Each site will keep a confidential, site – only log of enrolled patients connecting their identity to a coded subject identifier. Each subject will be entered on the log along with procedure date and will be assigned a patient study number comprised of the site number and sequential subject number enrolled. This coded number will be used in the CRFs. For example, John Q Doe, the 12th patient enrolled at site number 2, will be assigned study identifier 002-012. All activities will be performed in compliance with HIPPA and Good Clinical Practice standards

#### Data Center

CRFs or coded anonymized data will be forwarded to the Central Data Center, checked for completeness, and entered in the Database as received. Incomplete forms will be returned to the study site for completion. Electronic submission of Data may be employed, but is not required.

See the "Study Statistical Plan" for a description of the plan.

## **IX. ETHICAL, REGULATORY & ADMINISTRATIVE REQUIREMENTS**

The devices being studied in this clinical plan, and the tests performed under it, are approved for marketing by the US-FDA for use as described and have been in use for cardiac catheterization procedures at the participating institutions. FDA approval of the study is not required. No part of the study uses any device or test that is considered investigational.

### Investigational Review Board Approvals.

Data from this study may be used for publication in the scientific literature, and therefore IRB approval is required. No patient may be enrolled until IRB approval is granted, and an Informed Consent approved by the IRB is signed by the subject.

### Protocol Adherence and Amendments

Investigators will be required to adhere to the protocol requirements. Deviations or violations of the protocol may result in dismissal from the study.

### Informed Consent

Each subject in the study must sign the informed consent agreeing to participation.

### Alternatives to Participation

As a voluntary randomized study, the patient's alternative to participation is primarily to the local standard of care, typically involving the Perclose alone or Perclose with manual compression, used per local protocol. SS devices may be used outside of the study depending on local practice and availability.

### Enrollment in other studies

Simultaneous or dual enrollment in other investigative or observational protocols that do not involve vascular access, anticoagulation, or antiplatelet agents is expressly permitted. The interventions in this trial are not expected to significantly impact upon the outcomes of other protocols, however, the site investigator is responsible for ensuring that there is no conflict with dual enrollment from the standpoint of the other trial.

### Study Activities

The Investigator is required to perform the study in accordance with the protocol and to use devices per their instructions for use.

### Follow-Up

There is no requirement for the subjects taking part in the study to be seen or examined for any follow up relative to the study following completion of activities described herein.

### CRFs

CRFs will be completed for each subject. See Appendix 1 for the CRFs.

### Records and Retention

Copies of all records will be retained by the investigator at each site for 2 years.

### (Model) Patient Informed Consent

See Appendix 2

### Communication with the Principal Investigator:

All communication regarding the study should be routed directly to the Principal Investigator. Copies of all correspondence regarding the study should be maintained in the Site Investigator study file.

#### Declaration of Helsinki & HIPPA

The Principal Investigator will ensure that this study is performed in conformity with the Declaration of Helsinki, HIPPA, and all local and national regulations.

#### Investigator Responsibilities

- Adhere to all of the required elements of the Clinical Protocol
- Resolve queries in a timely manner
- Participate in Investigator meetings and emails, if scheduled
- Comply with the Declaration of Helsinki
- Obtain written Informed Consent from each study participant before any study specific procedures are performed
- Complete all required case report forms (CRFs) for each subject
- Comply with all applicable regulations and codes of approvals from the site IRB and other Regulatory Authorities
- Notify the Principal Investigator of personnel changes that may affect the study protocol
- Retain all records and study files as required, after which the files may be destroyed.
- Allow direct access to source data/documents, including patient records, in case of monitoring, auditing and/or inspection by the IRB and/or other regulatory authority bodies.

## **X. RISK BENEFIT ANALYSIS**

#### General Risks and Presumed Benefits:

Application of a hemostatic device in a setting absent an actual femoral arteriotomy presents negligible risk to the subject.

Patients assigned to the SS group may enjoy less discomfort from the shorter length of time needed to lay flat as compared to the Perclose being placed by itself, presuming that the SS does reduce the time to ambulation.

The potential benefit of subject participation is gratification from making a contribution to science helping to demonstrate the effectiveness of a new clinical method to achieve hemostasis following a femoral artery procedure. This new method could potentially provide a safer, more efficient, and more effective hemostatic device for clinicians to use in treating patients undergoing the femoral artery approach for cardiovascular procedures.

#### Risks related to Perclose Device:

Currently marketed Perclose devices have been associated with complications such as, but not limited to, skin irritation, femoral artery or branch occlusion, arterial dissection, hematoma, pseudoaneurysm, failure to achieve hemostasis, and general groin discomfort.

#### Risks Specific to the Study Device:

There are no known risks specific to the study device.

#### Risk Mitigation:

Every effort will be made to mitigate risks in this Study. Those efforts include requiring investigators to be highly experienced operators.

Clinical monitoring will occur in real time to ensure the accurate collection and reporting of data, and ensure that the Site is in compliance with the clinical protocol requirements that mitigate risk

such as patient entry criteria, use of the study device in accordance with instructions, and compliance with study test procedures and methods.

#### **APPENDICES:**

Appendix 1: Sample Patient information sheet

Appendix 2: CRF's
